7.3 Clinical Laboratory Tests

Standard clinical safety laboratory (chemistry and hematology) collected at the Medical Screening Visit (Visit 1) and the second Treatment EEC Session (Visit 4) as part of study exit procedures include following parameters:

- Hematology profile: hemoglobin, hematocrit, red blood cell (RBC) count, white blood cell (WBC) count, and absolute platelet count
- Serum chemistry profile: albumin, alkaline phosphatase (ALP), ALT (SGPT), AST (SGOT), BUN, calcium, carbon dioxide (CO₂), chloride, total cholesterol, creatinine, creatinine phosphokinase (CPK), glucose, phosphate, potassium, sodium, total protein, and uric acid.

All laboratory tests including pregnancy testing will be provided. Separate listing will also be provided for clinically significant abnormal laboratory values.

7.4 Vital Signs

Vital sign assessments will be taken with the subject in the sitting or supine position after 5 minutes at rest and will include body temperature, pulse rate, blood pressure (BP), and respiratory rate (RR) prior to EEC entry and at end of Visit 4 prior to study exit.

Observed and changes from baseline for vital signs will be summarized by visit. Baseline is defined as the last non-missing measurement taken prior to the first dose.

Listing will be provided for ITT Population.

8. Efficacy Analysis

The efficacy evaluation will be performed to assess the activity of Reproxalap Ophthalmic Solution based on the subjects reported ocular itching using a standard 9-point scale (0-4 scale with 0.5-unit increments) and tearing on a standard 4-point (0-3 scale) and trained staff assessed conjunctival redness using a standard 9-point scale (0-4 scale with 0.5 unit increments).

For all staff assessed and subject reported symptoms where values from both eyes are obtained at the same timepoint, the average score from both eyes will be used for analysis.

The following analysis will be performed for all efficacy endpoints using ITT Population:

- Observed and changes from baseline by visit and treatment
- Analysis using Mixed Model Repeated Measures (MMRM) using all available data collected during the EEC
- Plots for mean score over time, and mean changes of score from baseline over time

The onset of action time point and the duration of action will be reported for each efficacy endpoint whenever applicable. Duration of action will be the longest (in minutes) series of time points over which majority is statistically significant in favor of test drug, including the first and last time points in the series. Onset of action will be the first time point in the duration series. If two or more duration series are equivalent in length (in minutes), then the onset will be the first time point in the series that occurs earliest.

Subjects' assessment at Screening EEC and Post-EEC exit time points will be listed ONLY. All efficacy data will be listed for ITT Population.

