## **10.6 Primary Efficacy Analysis**

The efficacy analyses of all efficacy endpoints will be carried out in the ITT population. Supportive analyses may also be provided for Itching endpoint(s) using the PP population.

Descriptive statistics of all activity endpoints as well as individual data listings will be presented by treatment group and efficacy measures.

For the primary efficacy endpoint, treatment comparisons will be made between Reproxalap Ophthalmic Solution (0.25%) and vehicle. The treatment comparisons will be performed at pre-specified time points (every 10 minutes from 110 minutes to 210 minutes following chamber entry) by using a Mixed Model Repeated Measures(MMRM) approach for a crossover study with two periods.

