6.1 General Statistical Procedures

Frequency distributions for categorical variables will be provided as number of patients in the category and the percentages of the total number of patients in the given population as noted. Percentages will be reported to one decimal place.

The descriptive statistics for continuous variables will be number of subjects (n), mean, standard deviation (SD), median, minimum and maximum. Mean and median will be reported to 1 more decimal place than the raw data, while the SD will be reported to 2 more decimal places than the raw data. Minimum and maximum will be reported the same as the original data.

All statistical tests will be two-sided with a significance level of 0.05 ($\alpha = 0.05$) unless otherwise specified. Confidence interval (CI) for differences between treatment will be two-sided at 95% confidence interval.

P-value will be rounded to at most 3 decimal places and will be reported as < 0.001 if it is smaller than 0.001.

Unless otherwise specified, subjects' characteristics at baseline will be summarized by treatment sequences (Reproxalap 0.25%/Vehicle, Vehicle/Reproxalap 0.25%). Safety and efficacy will be summarized by treatment (Reproxalap 0.25%, Vehicle) where appropriate.

In general, all listings will be ordered by subject number and visit for available data unless otherwise specified in the text.

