8.2 Key and Secondary Efficacy Analysis

The key secondary efficacy endpoint is

- Change from baseline in conjunctival redness on a 9-point scale (0-4) during the chamber (approximately 10 to 210 minutes)

The secondary efficacy endpoints are

- Change from baseline in tearing on a 4-point scale (0-3) during the chamber (approximately 10 to 210 minutes)
- Change from baseline in TOSS on an 11-point composite score (sum of itching, tearing, and redness) during the chamber (approximately 10 to 210 minutes)

TOSS will be derived as the sum of ocular itching, conjunctival redness and tearing symptoms at each time point.

Observed and changes from baseline duration treatment EEC session will be summarized by visit and treatment for ITT population.

All secondary efficacy endpoints will be analyzed using a similar approach as the primary efficacy variable for the ITT Population. Reproxalap Ophthalmic Solution will be claimed to be better than Vehicle on secondary efficacy endpoints if the estimated overall corresponding changes from baseline score from MMRM model in the Reproxalap group is statistically lower than that of the Vehicle group during the chamber (approximately 10 to 210 minutes).

[REDACTED]

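### In its visible text, SAP section 8 reports onset and duration of action for each efficacy endpoint from time-point significance, with no stated link to that endpoint's own success criterion and no minimum series length

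*SAP*

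**What the plan says.** The rule stands in the opening text of SAP section 8 (Efficacy Analysis), before 8.1, in a paragraph with no visible redaction.

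- Scope: "The onset of action time point and the duration of action will be reported for each efficacy endpoint whenever applicable". The closing qualifier is not defined.
- Duration: "Duration of action will be the longest (in minutes) series of time points over which majority is statistically significant in favor of test drug". The first and last points of the series are included.
- Onset: "Onset of action will be the first time point in the duration series".
- Test level, SAP 6.1: "All statistical tests will be two-sided with a significance level of 0.05", unless otherwise specified. Section 8 specifies nothing else for the time-point tests.

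The efficacy endpoints are itching, redness, tearing and TOSS. TOSS is not a separate measurement: "TOSS will be derived as the sum of ocular itching, conjunctival redness and tearing symptoms at each time point". The model is an "Analysis using Mixed Model Repeated Measures (MMRM) using all available data collected during the EEC".

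The claim criteria are elsewhere. SAP 8.1 and 8.2 say when reproxalap will be claimed better than vehicle, and both rest on the MMRM estimate. The onset and duration paragraph does not refer to either.

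**The concern.** An onset of action presupposes an action. Followed as written, the rule can produce a report in which an endpoint misses its criterion in 8.1 or 8.2 and is still given a time of onset and a duration in minutes. The search runs over many time points and four endpoints, so under no effect a qualifying series turns up more often than a favourable overall test would.

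SAP section 6 adds to this. It treats every analysis in the plan as a priori and keeps the exploratory label for analyses designed after database lock. An onset found this way would therefore appear as a pre-specified result without a caveat. What is at stake is how a reader interprets the reported onset and duration, not the trial's efficacy decision.

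**Working it through.** The plan gives no error rate for onset or duration, so there is no figure to reproduce. The question is how often the rule yields an onset when the product has no effect.

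**Inputs from the documents**
- Two-sided 0.05 per test (SAP 6.1), so 0.05 / 2 = 0.025 in the drug's favour at each time point.
- Four endpoints, with TOSS the sum of the other three (SAP 8.2).
- Primary window for itching: "every 10 minutes from 110 minutes to 210 minutes following chamber entry" (Protocol 10.6), which is (210 − 110)/10 + 1 = 11 points.

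**Assumptions**
- 21 points per endpoint over the session: (210 − 10)/10 + 1 = 21. The schedule tables are not shown, and redness runs on a slightly different clock (12 to 212 minutes).
- Time-point test statistics correlated 0.5 to 0.9 (exchangeable) or 0.9 to 0.95 per 10 minutes (AR(1)).
- Correlation between itching, redness and tearing varied around 0.5, with TOSS as their equally weighted sum.

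**Upper bound under independence**
- P(at least one significant point) = 1 − (1 − 0.025)^m.
- m = 21: 1 − 0.975^21 = 0.412.
- m = 11: 1 − 0.975^11 = 0.243.

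**Correlated case**

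Null multivariate normal statistics were simulated (200,000 replicates for one endpoint, 100,000 for four). A point is significant if z > 1.96. A series qualifies if its first and last points and more than half of its points are significant. The overall test is the standardized mean over time points. The column headed *overall fails* gives the chance of an onset together with a failed overall test.

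| Correlation, 21 points | Onset, one point counts | Onset, two points needed | Onset and overall fails (one / two points) | Any of four, one point: between-endpoint 0.3 / 0.6 | Any of four, two points: 0.3 / 0.6 |
|---|---|---|---|---|---|
| Exchangeable 0.5 | 0.217 | 0.057 | 0.192 / 0.034 | 0.478 / 0.410 | 0.161 / 0.136 |
| Exchangeable 0.7 | 0.148 | 0.056 | 0.123 / 0.031 | 0.348 / 0.293 | 0.151 / 0.127 |
| Exchangeable 0.9 | 0.078 | 0.044 | 0.053 / 0.019 | 0.203 / 0.168 | 0.124 / 0.102 |
| AR(1) 0.9 | 0.161 | 0.099 | 0.136 / 0.074 | 0.383 / 0.322 | 0.255 / 0.214 |
| AR(1) 0.95 | 0.113 | 0.079 | 0.088 / 0.055 | 0.283 / 0.235 | 0.210 / 0.173 |

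At between-endpoint correlation 0.5, the chance of an onset on at least one of four endpoints is 0.43, 0.32 and 0.18 for exchangeable 0.5, 0.7 and 0.9, and 0.34 for AR(1) 0.9, if one point counts. If two are needed it is 0.11 to 0.23.

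Against the 0.025 for a favourable overall test, the single-endpoint rate is 0.078/0.025 = 3.1 to 0.217/0.025 = 8.7 times as large if one point counts, and 0.044/0.025 = 1.8 to 0.099/0.025 = 4.0 times if two are needed.

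**Sensitivity**

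With 11 points under the same correlations, the single-endpoint rate is 0.065 to 0.151 (one point) or 0.036 to 0.058 (two points).

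**With a gate**

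If an onset is reported only when the overall test favours the drug, the single-endpoint rate is at most 0.025. Over four endpoints it is about 0.065 at between-endpoint correlation 0.5.

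**The case against.** Four counter-arguments deserve weight.

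1. *Unseen text.* SAP 8.1 is redacted directly after the primary criterion and again after the non-convergence rule, 8.2 ends in a redaction, and only the heading of Protocol 10.10 (Adjustment for Multiplicity) is available. A reader might infer that the time-point tests are definitely unadjusted and ungated. The documents do not support that; it can be said only of the visible text. Even so, the rule stands outside those sections and points to none of them, so a gate placed there would still need a cross-reference.

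2. *Not a claim.* A reader might infer that the trial's type I error is inflated. It is not. Onset and duration are not listed as endpoints and are not in the hypotheses of Protocol 10.2, and the claim criteria rest on the MMRM estimate. This stands in full, and it limits the point to reporting.

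3. *The qualifier may be a gate.* It could mean that an effect has been shown. It could also mean only that a qualifying series exists, which is the more natural reading given the definitions that follow. The SAP does not say which.

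4. *The larger rates need a one-point series.* A series with a first and last point and a length in minutes suggests more than one point, and one point would give a duration of 0 minutes. A reader might infer that any given endpoint would often receive a false onset. With two points needed, that is not so: about 0.04 to 0.10. Nothing in the definition excludes a single point, however, and even the two-point rates exceed 0.025.

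**Conclusion.** The point holds as a gap in a reporting rule. As visible, SAP section 8 can assign an onset and duration to an endpoint that fails its own test. Under no effect this combination arises in about 5% to 19% of trials per endpoint if one point counts, or about 2% to 7% if two are needed.

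These sizes rest on 21 time points and on correlations that the documents do not give. The choice between one and two points matters as much as the correlation does, and the SAP leaves it open. A change before database lock is worthwhile, but the trial's conclusions on efficacy do not depend on it.

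**What to change.** In SAP section 8:

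- Replace the undefined qualifier with: *only for endpoints that meet their own pre-specified success criterion in 8.1 or 8.2 in favor of reproxalap; otherwise onset and duration will be reported as not established*.
- State that a series needs at least two time points.
- Label onset, duration and time-point p-values as descriptive and not adjusted for multiplicity.

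The gate should name each endpoint's own criterion rather than a single overall MMRM contrast. For itching, Protocol 10.6 describes comparisons at time points, whereas Protocol 10.7 ties a single treatment p value to the secondary endpoints, and the itching criterion in SAP 8.1 is followed by redaction. The visible text therefore does not establish one overall contrast for itching.

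If the redacted text already contains a gate, a cross-reference in section 8 is enough for that part.

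The cost is a few sentences. The downside is that no onset or duration is reported for an endpoint that fails its own test. The gate also leaves about 0.065 over four endpoints (computed with the overall contrast as the gate), because it works endpoint by endpoint; the descriptive label is needed for that reason.

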8.1 Primary Efficacy Analysis

The primary efficacy endpoint is the change from baseline (pre-dose) in ocular itching scores on a 9-point scale (0-4 scale with 0.5-unit increments) from 110-212 minutes between Reproxalap Ophthalmic Solution (0.25%) and vehicle.

Observed and changes from baseline duration treatment period will be summarized by visit and treatment for ITT, PP, and Completer populations.

Primary efficacy analyses will be carried out in the ITT population. Supportive analyses for primary efficacy endpoint will also be provided using the PP population and the Completer population if more than 10% of ITT population is excluded from PP population.

The treatment comparison will be performed by using a Mixed Model Repeated Measures (MMRM) approach for a crossover study with 2 treatment periods (Visit 3 treatment EEC Session One and Visit 4 treatment EEC Session Two).

[REDACTED]

[REDACTED]

[REDACTED]

Reproxalap Ophthalmic Solution will be claimed to be better than Vehicle if the estimated change of ocular itch score from baseline based on MMRM model in the Reproxalap group is statistically lower than that of the Vehicle group

[REDACTED]

If the MMRM model does not converge with any correlation structure, then a within-subject t-test (baseline-adjusted, if useful) will be used to compare the score difference across treatment groups at each time point.

[REDACTED]

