### 5.2 Discontinued Subjects

Subjects may be discontinued prior to their completion of the clinical trial due to:

- Subject request/withdrawal;
- AEs;
- Positive COVID-19 test result;
- Positive pregnancy results;
- Protocol violations;
- Administrative reasons (e.g., inability to continue, lost to follow-up);
- Sponsor termination of the clinical trial;
- Any sound medical reason, as determined by the investigator; or
- Other.

Notification of a subject discontinuation and the reason for discontinuation will be made to the Sponsor or designee and will be clearly documented on the eCRF. Subjects who are discontinued from the clinical trial will not be replaced.

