## **10.2 Statistical Hypotheses**

The following hypotheses will be tested comparing reproxalap to vehicle in this cross-over design. The null hypotheses must be rejected for the dosing regimen to claim efficacy.

H0: There is no difference between reproxalap and vehicle in the change from baseline in Ocular Itching score on a 9-point scale (0-4) from 110-210 minutes.

H1: The change from baseline in Ocular Itching score on a 9-point scale (0-4) is smaller with reproxalap than with vehicle in the ITT population from 110- 210 minutes.

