## **10.3 Sample Size**

Approximately 670 subjects with ragweed-induced, moderate-to-severe allergic conjunctivitis will be screened in the EEC in order to randomize approximately 126 subjects, and for 100 subjects to complete the study. Approximately sixty-three (63) subjects will be assigned to each of two (2) treatment sequences, AB and BA.

Prior to database lock, the Sponsor will finalize a statistical analysis plan (SAP) that will detail all planned analyses and will dominate any statistical analysis herein. Any analyses conducted in addition to those specified in the SAP will be clearly documented as post hoc.

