2.2 Sample Size

Approximately 670 subjects with ragweed-induced, moderate-to-severe allergic conjunctivitis will be screened in the EEC in order to randomize approximately 126 subjects, and for 100 subjects to

complete the study. Approximately sixty-three (63) subjects will be assigned to each of two (2) treatment sequences, AB and BA.

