2.3 Randomization and Masking

2.3.1 Randomization

Eligible subjects will be randomized 1:1 to one of two treatment sequences of AB or BA where:

- Treatment A: Reproxalap Ophthalmic Solution (0.25%)
- Treatment B: Vehicle Ophthalmic Solution [REDACTED]

Approximately 126 subjects (approximately 63 per treatment sequence) will be enrolled.

Each subject screened for the clinical trial will be assigned a unique subject number that will be used to identify the subject throughout subject participation in the clinical trial. If a subject fails to be randomized, the reason should be documented in the source documents and case report form (CRF). The subject will be considered a screen failure.

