5.3 Intent-to-Treat (ITT) Population

ITT Population includes all randomized subjects who use at least one dose of investigational drug and have any post-dose assessments. Subjects are evaluated according to the investigational drug treatment of the visit as per the randomized treatment sequence.

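### If the MMRM fails to converge, the SAP 8.1 fallback (a within-subject t-test) cannot use one-session subjects, so the ITT primary analysis becomes in effect a completers analysis

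*SAP*

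**What the plan says.** SAP 8.1 states the analysis set without qualification: "Primary efficacy analyses will be carried out in the ITT population". SAP 5.3 defines that set broadly: "ITT Population includes all randomized subjects who use at least one dose of investigational drug and have any post-dose assessments". A subject who is dosed and assessed at Visit 3 but never reaches Visit 4 is therefore in ITT.

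The planned analysis is an MMRM for a two-period crossover, and the opening of SAP 8 says that it uses all available in-chamber data. SAP 8.1 then gives a fallback. If no correlation structure converges, "then a within-subject t-test (baseline-adjusted, if useful) will be used to compare the score difference across treatment groups at each time point". The readable text names no separate analysis set for this fallback.

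Three other statements bear on it:
- SAP 4.2 says that missing data are generally not imputed.
- Protocol 10.3 plans the numbers "in order to randomize approximately 126 subjects, and for 100 subjects to complete the study", and SAP 2.2 repeats them.
- Protocol 5.2 says of dropouts: "Subjects who are discontinued from the clinical trial will not be replaced".

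SAP 5.4 separately defines a Completer population, those dosed at both treatment visits. SAP 8.1 gives that population a supportive role only.

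**The concern.** The MMRM and its fallback do not analyse the same people. The MMRM can use a Visit 3 score from a subject who has no Visit 4 score. A within-subject t-test works on the difference between a subject's two scores, so that subject has no value to enter. If the fallback were triggered, the primary analysis would move from ITT to something close to the Completer population, and no readable sentence says so.

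Two things are at stake. Some precision is lost with the unpaired data. There is also exposure to selection: those who remain may have been selected on one of the two scores being subtracted. In addition, the supportive Completer analysis would then rest on nearly the same subjects as the primary one, and would no longer check it.

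**Working it through.** **Inputs from the documents.** About 126 randomized and 100 completing (Protocol 10.3, SAP 2.2). Allocation: "Eligible subjects will be randomized 1:1 to one of two treatment sequences of AB or BA", about 63 per sequence. No replacement (Protocol 5.2). Generally no imputation (SAP 4.2).

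**Inputs assumed.** The readable text gives no effect size, SD, correlation or dropout pattern. I take unit SD, a within-subject correlation ρ of 0.3 to 0.7 and, for illustration, a true difference of -0.50 SD. The planned 126 cannot be re-derived from visible inputs. It is consistent with 100 completers and about 20% loss, since 100/0.80 = 125.

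**Step 1: how many could be affected.** 126 - 100 = 26, and 26/126 = 20.6%. This is an upper planning figure:
- Protocol 5.1 defines completion as not having been discontinued, not as having paired scores.
- A randomized subject with no dose or no post-dose assessment is outside ITT altogether.
- A subject who leaves during Visit 4 still has pairs at the earlier time points.

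**Step 2: precision.** Take 100 pairs (50 per sequence) and 13 Visit 3-only subjects per sequence.
- Variance of the paired difference: 2(1 - ρ)/100.
- Variance of the between-subject contrast from the one-session subjects: 1/13 + 1/13 = 0.1538.
- A model that keeps everyone combines the two by inverse variance.

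| ρ | Paired variance | All-subject variance | SE ratio, paired to all |
|---|---|---|---|
| 0.3 | 0.0140 | 0.01283 | 1.045 |
| 0.5 | 0.0100 | 0.00939 | 1.032 |
| 0.7 | 0.0060 | 0.00577 | 1.019 |

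For ρ = 0.5: 1/0.0100 + 1/0.1538 = 106.5, so the variance is 0.00939 and the ratio is √(0.0100/0.00939) = 1.032.

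**Step 3: bias if leaving depends on the Visit 3 score.** Write the difference as reproxalap minus vehicle. It is Visit 3 minus Visit 4 in AB, and Visit 4 minus Visit 3 in BA. Suppose that removing subjects with high Visit 3 scores lowers the mean Visit 3 score of those who stay by δ. Their mean Visit 4 score then falls by about ρδ. The difference shifts by -(1 - ρ)δ in AB and by +(1 - ρ)δ in BA.
- *Equal losses and equal selection in each sequence:* the shifts cancel. Simulation with 13 lost per sequence gives a paired mean of -0.498 to -0.501 against a true -0.50.
- *Leaving driven by the raw Visit 3 score (logistic slope 1 to 2 per SD):* if the drug works, Visit 3 scores are higher in BA, so more BA subjects leave (about 15-16, against 10-11 in AB). The BA shift dominates and the paired mean is -0.470 to -0.493, which is 6% to 1% closer to zero. A random-intercept model on all subjects stays at about -0.50.

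**The case against.** The strongest reply is that this is a remote contingency with a small price. The fallback needs failure under every correlation structure. The SAP abbreviations include first-order autoregressive and compound symmetry, which have very few parameters and seldom fail. The standard error grows by only 2-4%, and any attenuation is toward no effect, which is conservative for a superiority claim. Text on both sides of the fallback sentence is blacked out, and the body of Protocol 10.9 on missing data is not shown, so a rule for unpaired subjects may exist there. All of this stands. It keeps the point minor, but it does not remove the conflict between the fallback and the stated analysis set.

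A reader might also infer three stronger things that the documents do not support.

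- **A multiplicity fault.** Protocol 10.2 frames the null over a window ("H0: There is no difference between reproxalap and vehicle in the change from baseline in Ocular Itching score on a 9-point scale (0-4) from 110-210"), so tests at each time point could look like an uncontrolled family. However, Protocol 10.6 and the synopsis describe the primary comparison itself at 10-minute time points, so a pointwise fallback mirrors it. How the time points combine into a claim is not visible: SAP 8.1 is partly blacked out and the body of Protocol 10.10 is not shown. Any error rate or power figure would price a decision rule that the readable text does not contain.
- **A paired estimate that is always biased.** Step 3 shows that it is not when losses are equal between sequences.
- **One-session data disappearing from view.** SAP 8 plans ITT summaries and listings of all efficacy data in any case.

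**Conclusion.** The point holds as a minor, conditional inconsistency. On the readable text, the fallback cannot be carried out in the population that SAP 8.1 names for the primary analysis.

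Its reach is at most about 26 of 126 subjects (20.6%). The plan does not say that 26 will lack a second session, so that number should be read as a ceiling drawn from approximate planning figures. The precision cost is about 2-4% in standard error for correlations of 0.3 to 0.7. Attenuation is about 1-6% if leaving follows the Visit 3 score and losses are unequal between sequences, and nil if they are equal. The correlations, the effect size and the strength of selection are assumptions. The planned MMRM is unaffected. If the blacked-out text already provides for one-session subjects, confirming that settles the matter.

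**What to change.** In SAP 8.1, replace the within-subject t-test with a simpler likelihood model that keeps the ITT population. Suggested wording:

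*If the MMRM does not converge under any correlation structure, change from baseline will be analysed by a linear mixed model (REML) with treatment and period as fixed effects and subject as a random intercept. The model will be fitted in the ITT population, including subjects with data from one session only, at the same time points or over the same window as the primary MMRM contrast. A within-subject t-test will be reported as a supportive analysis in the Completer population.*

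If the window version is used, also state how a session value is formed when single time points are missing.

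The cost is a short SAP edit and a few lines of code, with no new data. With at most two values per subject in each fit, the model should rarely fail. The small downside is that one-session subjects enter under a missing-at-random assumption, which the MMRM already makes.
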